The key secondary endpoint of PFS will be summarised by Kaplan-Meier plots presented by treatment groups. Median PFS and the proportion of patients who are progression-free at 3, 6, and 12 months will be summarised along with 80% confidence intervals presented for each treatment group. Patients who have not progressed by the time of the data cut-off for the updated analysis will be censored. The comparison between the treatment groups of PFS will be performed by fitting a Cox proportional hazard model with treatment group as the only covariate. The hazard ratio for PFS, based on the profile partial likelihood from the fitted using Cox proportional hazards model, will be calculated as a measure of the treatment effect along with the respective 95% Wald confidence interval and the asymptotic p-value from the Wald test for the difference in the log hazards in the fitted model.

The secondary endpoint of OS will not be formally compared between the groups but will be summarised in a Kaplan-Meier plot together with descriptive statistics, as described for PFS.

The secondary endpoints of ORR, DoR, and DCR will be summarised using descriptive statistics for each treatment group and associated 90% Agresti-Coull confidence interval.

For the key secondary endpoints of numbers of CAFs, CD8⁺ TILs, and regulatory T-cells, and the secondary endpoint of PD-L1 expression analysis in tumour tissue, it is hypothesised based on the mode of action of setanaxib that there will be a reduction in CAFs level and an increase in the number of CD8⁺ TILs. Data will be summarised descriptively and will be graphically presented by boxplots displayed for each treatment group and individual patient profiles displaying pre- and post-doses counts. Changes within treatment groups (ie, across paired tissue samples) and between treatment groups will be summarised. An ANCOVA model will be used to assess for significant differences after adjustment for Baseline differences. The treatment effect from the fitted ANCOVA model will estimate the treatment difference based on mean score. A logarithmic transformation will be applied prior to analysis, if appropriate.

For the secondary endpoint of changes in patterns of gene expression and differential gene expression in tumour tissue, data will be displayed graphically and will be assessed by principal components analysis to identify distinction between clusters of genes.

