6.1.2 Minor Changes

- Section 8 of the protocol only discusses an estimand and intercurrent events related to the primary objective. The estimand framework has been built in Section 9.0 of this SAP for all the secondary objectives related to estimation of the treatment effect.
- Section 8.4.6 of the protocol describes a summary of abnormal physical examination findings should be presented. During the review of the initial SAP draft, the study team decided that a listing of all findings would be sufficient.
- Section 8.4.6 of the protocol also describes discrepancies between randomisation stratification information (obtained from IRT) and strata formed based on Screening factor collected on eCRFs (HPV status) will be explored. The HPV status on the CRF Randomisation page is integrated from the IRT data and so this presentation isn't necessary.
- Section 8.4.6 of the protocol also describes a presentation of modified World Health Organisation (WHO) ratings. These ratings are not collected for this study, hence no presentations will be provided.
- Section 8.2 of the protocol define the PK analysis set as "...all patients who receive at least 1 dose of setanaxib and have at least 1 measured concentration at a scheduled PK time point post-dose." A clarification was added to note that any concentration below the quantification limit (BQL) is considered to be a measured concentration and therefore included.

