9.0 Study Estimands

An estimand is a precise description of the treatment effect reflecting the clinical question posed by a given clinical trial objective. The estimand consists of five attributes: the treatment, the population, the variable, the specification of intercurrent events and how to account for these, and the population level summary.

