 To assess the ORR, the DoR and DCR per RECIST v1.1 in recurrent or metastatic SCCHN patients treated with setanaxib and pembrolizumab versus patients treated with placebo and pembrolizumab 	 Variables: ORR: Proportion of the patients who have a CR or PR per RECIST v1.1. DCR: Proportion of the patients in whom the best overall response is determined as CR, PR, or SD per RECIST v1.1. Intercurrent Events: Premature study discontinuation Use of certain alternative or additional therapy including a new anti-cancer therapy PD or Death Premature study drug discontinuation/interruption
	 Strategy: Hybrid (While on Treatment / Treatment Policy) A While on Treatment approach will be taken to address the first 3 intercurrent events. Any values for the variable of interest after the occurrence of the intercurrent events listed are considered irrelevant in defining the treatment effect of interest, i.e. only values prior to the occurrence of the intercurrent event are considered. A Treatment Policy approach will be taken where patients prematurely discontinue/interrupt study treatment. The value for the variable of interest is used regardless of whether or not the intercurrent event occurs. Population Level Summary Measure: ORR and DCR: The summary measure of associated 90% Agresti-Coull confidence interval of ORR and DCR at each treatment group.
	 Variable: DoR: The minimum time when CR or PR is first observed to the time of PD or death. Intercurrent Events: Premature study discontinuation Use of certain alternative or additional therapy including a new anti-cancer therapy Premature study drug discontinuation/interruption Strategy: Hypothetical A hypothetical strategy will be applied using censoring rules (see Section 10.9.4). Population Level Summary Measure: DoR: Kaplan Meier estimates of the median and quartiles along with their 90% CIs using the Brookmeyer-Crowley method.

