12.5.4.1 Objective Response Rate (ORR) and Disease Control Rate (DCR)

The point estimates of ORR and DCR (see Sections 10.9.3 and 10.9.5 respectively) will be summarised using descriptive statistics along with associated 90% Agresti-Coull CIs for each treatment group.

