12.5.4.2 Duration of Response (DoR) and Overall Survival (OS)

The secondary endpoints of DoR and OS will not be formally compared between the treatment groups, but will be summarised using Kaplan-Meier plots presented by treatment group.

Specifically, for OS, the median, upper quartile, lower quartile OS and the proportion of patients who are alive at 3, 6, and 12 months will be presented along with 80% Wald CIs, obtained using the Brookmeyer-Crowley method (1982).

DoR will only be presented if there are at least 5 responders in either treatment group, otherwise this data will be listed only.

Censoring rules for both DoR and OS are described in Sections 10.9.4 and 10.8.2 respectively.

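### ORR and DCR have a versus-placebo objective and a treatment-effect estimand, but only per-arm intervals are planned, so the between-arm effect is left unestimated

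*Protocol*

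**What the plan says.** **Objective.** Protocol Summary, Protocol 2.2 and SAP 7.2 all frame ORR, DoR and DCR as one treatment versus the other. SAP 9.1.2 repeats it: "To assess the ORR, the DoR and DCR per RECIST v1.1 in recurrent or metastatic SCCHN patients treated with setanaxib and pembrolizumab versus patients treated" (the comparator is the placebo arm).

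**Analysis.** The Protocol Summary and Protocol 8.4.3 state: "The secondary endpoints of ORR, DoR, and DCR will be summarised using descriptive statistics for each treatment group and associated 90% Agresti-Coull confidence interval". SAP 12.5.4.1 says the point estimates of ORR and DCR "will be summarised using descriptive statistics along with associated 90% Agresti-Coull CIs for each treatment group".

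**Estimand.** SAP 9.0 opens with: "An estimand is a precise description of the treatment effect reflecting the clinical question posed by a given clinical trial objective". SAP 6.1.2 says: "The estimand framework has been built in Section 9.0 of this SAP for all the secondary objectives related to estimation of the treatment effect". The population-level summary for these two endpoints in SAP 9.1.2 is then: "ORR and DCR: The summary measure of associated 90% Agresti-Coull confidence interval of ORR and DCR at each treatment group".

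**Neighbouring endpoints.** SAP 12.5.4.2 states: "The secondary endpoints of DoR and OS will not be formally compared between the treatment groups". For OS the protocol says the same. No such sentence covers ORR or DCR. For safety, PK and gene expression, SAP 9.1.2 says there is no treatment effect to estimate and therefore no estimand.

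**The concern.** The SAP separates objectives that estimate a treatment effect, which receive an estimand, from those that do not, which receive a statement that none applies. ORR and DCR are in the first group, yet their summary measure describes each arm and not the effect between arms. They are also not listed among the endpoints that will not be compared. The SAP did revisit the protocol sentence in question, since SAP 6.1.1 moves DoR to Kaplan-Meier, but it left ORR and DCR as they were.

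Response is close to the trial's rationale. Protocol 1.3 gives raising the proportion of patients who respond to pembrolizumab as a hoped-for benefit, and Protocol 1.2 says the results may inform further development and regulatory submission. Without a planned contrast, the method and confidence level for the response difference will be chosen after unblinding, or readers will judge two per-arm intervals by eye.

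**Working it through.** **Inputs from the documents.** 25 patients per arm, with a maximum of 70 in total, hence 35 per arm at 1:1 (Protocol 8.3). Response to checkpoint inhibitors of about 20% (Protocol 1.3) or about 15% (Protocol 1.2). Per-arm 90% Agresti-Coull intervals. 80% and 95% CIs for the primary endpoint (SAP 12.5.2.2).

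**Assumptions, not in the documents.** Every treated-arm rate, both DCR rates, and that all 25 or 35 patients per arm are evaluable.

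**Step 1: the plan's own figures.** The documents give no power or target effect for ORR or DCR. For the primary endpoint (difference 20, SD 30, 2-sided alpha 0.20), the noncentrality is 20 / (30 × √(2/25)) = 2.357. With 48 df the power is 85.4%, which agrees with the stated 85%. For PFS, 4 × (1.2816 + 0.8416)² / (ln 0.5)² = 37.5, hence 38 events, also as stated.

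**Step 2: one outcome, 5/25 on placebo and 10/25 on setanaxib.**

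Agresti-Coull, 90%: z = 1.645, z² = 2.706, adjusted n = 27.706, adjusted p = (x + 1.353) / 27.706, half-width = 1.645 × √(p(1 − p) / 27.706).
- x = 5: p = 0.2293, half-width 0.1314, interval 9.8% to 36.1%.
- x = 10: p = 0.4098, half-width 0.1537, interval 25.6% to 56.3%.

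These overlap. With 5/25 on placebo, separation needs 13/25 on setanaxib.

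Newcombe, 80%: z = 1.2816. Wilson limits are 0.1175 to 0.3195 for 5/25 and 0.2844 to 0.5280 for 10/25.
- Lower: 0.20 − √((0.40 − 0.2844)² + (0.3195 − 0.20)²) = 0.20 − 0.166 = 0.034.
- Upper: 0.20 + √((0.5280 − 0.40)² + (0.20 − 0.1175)²) = 0.20 + 0.152 = 0.352.

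The difference is +20 points, 80% CI +3.4 to +35.2. The same formula at 95% (z = 1.96) gives −5.3 to +42.2.

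**Step 3: exact enumeration of two independent binomials.** A is the share of trials whose 80% Newcombe interval lies above zero. B is the share whose 90% per-arm intervals separate in favour of setanaxib. Every trial in B is also in A here, so the share of A with overlapping intervals is 1 − B/A.

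| Per arm | Placebo v setanaxib | A | B | 1 − B/A |
|---|---|---|---|---|
| 25 | ORR 15% v 30% | 50.7% | 11.5% | 77% |
| 25 | ORR 20% v 35% | 46.2% | 11.4% | 75% |
| 25 | ORR 20% v 40% | 60.2% | 20.8% | 65% |
| 25 | ORR 20% v 45% | 73.0% | 33.0% | 55% |
| 25 | ORR 20% v 50% | 83.5% | 46.8% | 44% |
| 25 | ORR 20% v 60% | 95.7% | 73.2% | 24% |
| 35 | ORR 20% v 40% | 71.9% | 29.2% | 59% |
| 35 | ORR 20% v 50% | 91.9% | 62.2% | 32% |
| 25 | DCR 50% v 70% | 56.4% | 18.0% | 68% |

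**Step 4: no effect.** At 20% in both arms with 25 per arm, the 80% interval excludes zero in either direction in 20.7% of trials, and the per-arm 90% intervals separate in 1.3%.

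**The case against.** The descriptive treatment may be deliberate. The primary, PFS, CAF, CD8/regulatory T-cell and PD-L1 objectives are worded as comparing, while ORR, DoR, DCR and OS are worded as assessing. OS has the same assess-versus form and is expressly not compared, so the word versus does not by itself promise a contrast. Tumour response also has a comparative analysis already: Protocol 3.2 chose best percentage change for its greater power than ORR, and the primary ANCOVA gives a difference with 80% and 95% CIs. ORR and DCR are not key secondary endpoints, and no decision or sample size depends on them.

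Much of this stands, and it limits the weight of the point. It does not explain why the SAP wrote a treatment-effect estimand for ORR and DCR without an effect measure, or why the non-comparison sentence leaves them out. A difference with an interval is also compatible with a descriptive purpose.

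A reader might infer three stronger things that the documents do not support:
- **That a real response effect would usually be hidden.** Neither document uses interval overlap as a rule. SAP 10.9.3 and 10.9.5 report numbers and percentages by arm, so the difference can be computed. Overlap is also the minority outcome for large gains (44% at 50% v 20%, 25 per arm).
- **That the trial has its own 80% level for response.** The 2-sided 20% level is set for the primary endpoint and PFS only.
- **That overlap is the only way to compare the arms.** It is one informal way, and a poor one.

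**Conclusion.** The gap is real and modest. The plan states a comparative objective and a treatment-effect estimand for ORR and DCR and then provides no estimate of that effect, in either document.

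The figures show what per-arm intervals fail to convey to someone reading them side by side. At 25 per arm and 20% v 40%, about 60% of trials would have an 80% CI for the difference that excludes zero, about 21% would show separated per-arm intervals, and about 65% of the trials favouring setanaxib would still show overlap (59% at 35 per arm). They rest on an assumed treated rate, full evaluability and the document's approximate 20% for control. They measure an informal reading, not an error rate of a planned test. This is an inexpensive improvement to non-key secondary endpoints and does not threaten the primary result.

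**What to change.** In SAP 9.1.2, replace the population-level summary for ORR and DCR with the between-arm difference (setanaxib minus placebo). In SAP 12.5.4.1, and in Protocol 8.4.3 if it is amended, report that difference with 80% and 95% Newcombe or Miettinen-Nurminen CIs, the levels SAP 12.5.2.2 uses for the primary endpoint. Label it descriptive, with no p-value and no multiplicity adjustment. Keep the per-arm 90% Agresti-Coull intervals as support.

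If the sponsor does not want a contrast, the minimum is to extend the non-comparison sentence to ORR and DCR and to stop describing their per-arm summary as a treatment-effect estimand.

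**Cost.** About one sentence in the SAP and one row in an existing table, with no new data. The downside is two more unadjusted intervals. At the 80% level each excludes zero about 20% of the time when there is no effect, so the descriptive label has to appear in the table itself. Giving the 95% interval alongside helps: in the 5/25 v 10/25 example it includes zero.

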17.3 AP	PENDIX III – Medications or Substances to Be Avoided or Used
wit	h Caution During Treatment with Setanaxib126
17.4 AP	PENDIX IV – RECIST v1.1 Methodology134
LIST OF	TABLES
Table 1	Schedule of Assessments22
Table 2	Risk Assessment44
Table 3	Calculation of Safety Margins Based on 39-Week Repeat Dose Study
	in Dogs
Table 4	Type of Concomitant Medications to Avoid or Use with Caution with
	Setanaxib126
Table 5	Use with Caution – Concomitant Medications with Known Risk of QT
	Interval Prolongation or Increased Risk of Torsades de Pointes128
Table 6	Avoid Usage – Guidance on Specific Concomitant Medications to
	Avoid with Setanaxib129
Table 7	Use with Caution – Sensitive CYP2C9, CYP2C19, CYP2B6, OAT3,
	BCRP, and P-gp Substrates131
	-

LIST OF FIGURES

Figure 1	Study Schematic	1
----------	-----------------	---

LIST OF ABBREVIATIONS

ADL	activities of daily living
AE	adverse event
AESI	adverse event of special interest
ALP	alkaline phosphatase
ALT	alanine aminotransferase
ANCOVA	analysis of covariance
AST	aspartate aminotransferase
AUC	area under the concentration-time curve
AUC(0-24)-ss	area under the concentration-time curve over the last 24-h dosing interval at steady state
BID	twice daily
CAF	cancer-associated fibroblast
CCl ₄	carbon tetrachloride
CD8	cluster of differentiation 8
Cmax-ss	maximum plasma concentration at steady state
Cmin-ss	minimum plasma concentration at steady state
CPS	combined positive score
CR	complete response
CRO	contract research organisation
CSR	clinical study report
СТ	computed tomography
CTCAE	Common Terminology Criteria for Adverse Events
CTLA4	cytotoxic T-lymphocyte antigen 4
CV	coefficient of variation
СҮР	cytochrome P450
DBP	diastolic blood pressure
DCR	disease control rate
DoR	duration of response
EAPA	Europe, Asia-Pacific, and Africa
ECG	electrocardiogram

ECOG	Eastern Cooperative Oncology Group
eCRF	electronic case report form
EGFR	epidermal growth factor receptor
ЕоТ	end-of-treatment
EudraCT	European Union Drug Regulating Authorities Clinical Trials
FAS	Full Analysis Set
FoxP3	forkhead box P3
FSH	follicle-stimulating hormone
GCP	Good Clinical Practice
GGT	gamma-glutamyltransferase
HBcAb	hepatitis B core antibody
HBsAg	hepatitis B surface antigen
HDPE	high-density polyethylene
HIPAA	Health Insurance Portability and Accountability Act
HIV	human immunodeficiency virus
HPV	human papillomavirus
HPV ^{-ve}	HPV-negative
$\mathrm{HPV}^{\mathrm{+ve}}$	HPV-positive
IB	investigator's brochure
IC ₅₀	half maximal inhibitory concentration
ICF	informed consent form
ICH	International Council for Harmonisation
IDMC	Independent Data Monitoring Committee
IPF	interstitial pulmonary fibrosis
IEC	Independent Ethics Committee
IgG4	immunoglobulin G4
IMP	investigational medicinal product
IRB	Institutional Review Board
IRT	interactive response technology
IV	Intravenous(ly)

Ki	inhibition constant
LD	longest diameter
LFC	limit fold change
lsmeans	least-square means
mAb	monoclonal antibody
MedDRA	Medical Dictionary for Regulatory Activities
MDR2	multidrug resistance protein 2
MRI	magnetic resonance imaging
myCAF	myofibroblastic CAF
NADPH	nicotinamide adenine dinucleotide phosphate oxidase
NASH	nonalcoholic steatohepatitis
NOAEL	no-observed-adverse-effect level
NOX	NADPH oxidase
OAT3	organic anion transporter 3
OD	once daily
ORR	overall response rate
OS	overall survival
PBC	primary biliary cholangitis
PCR	polymerase chain reaction
PD	pharmacodynamics
PD	progressive disease
PD-1	programmed cell death 1
PD-L	PD-ligand
PDGF	platelet-derived growth factor
PEG	percutaneous endoscopic gastrostomy
PET	positron emission tomography
PFS	progression-free survival
P-gp	P-glycoprotein
РК	pharmacokinetics
РО	per os (orally)

PR	partial response
q3w	every 3 weeks
QoL	quality of life
QTL	quality tolerance limit
R/M	recurrent and/or metastatic
RBC	red blood cell
RECIST v1.1	response evaluation criteria in solid tumours version 1.1
ROS	reactive oxygen species
SAE	serious adverse event
SAP	statistical analysis plan
SBP	systolic blood pressure
SCCHN	squamous cell carcinoma of the head and neck
SD	stable disease
SD	standard deviation
SEER	Surveillance Epidemiology and End Results
sh	short hairpin
si	small interfering
αSMA	alpha smooth muscle action
SmPC	summary of product characteristics
SOC	system organ class
STAM	
STAN	stelic animal model
SUSAR	stelic animal model suspected unexpected serious adverse reaction
SUSAR T4	stelic animal model suspected unexpected serious adverse reaction thyroxine
SUSAR T4 TEAE	stelic animal model suspected unexpected serious adverse reaction thyroxine treatment-emergent adverse event
SUSAR T4 TEAE TGF-β	stelic animal model suspected unexpected serious adverse reaction thyroxine treatment-emergent adverse event tumour growth factor beta
SUSAR T4 TEAE TGF-β TIL	stelic animal model suspected unexpected serious adverse reaction thyroxine treatment-emergent adverse event tumour growth factor beta tumour-infiltrating lymphocyte
SUSAR T4 TEAE TGF-β TIL TLR	stelic animal model suspected unexpected serious adverse reaction thyroxine treatment-emergent adverse event tumour growth factor beta tumour-infiltrating lymphocyte toll-like receptor
SUSAR T4 TEAE TGF-β TIL TLR TSH	stelic animal model suspected unexpected serious adverse reaction thyroxine treatment-emergent adverse event tumour growth factor beta tumour-infiltrating lymphocyte toll-like receptor thyroid-stimulating hormone
SUSAR T4 TEAE TGF-β TIL TLR TSH UDCA	stelic animal model suspected unexpected serious adverse reaction thyroxine treatment-emergent adverse event tumour growth factor beta tumour-infiltrating lymphocyte toll-like receptor thyroid-stimulating hormone ursodeoxycholic acid

UGT	UDP-glucuronosyltransferase
ULN	upper limit of normal
US FDA	United States Food and Drug Administration
WBC	white blood cell

1 INTRODUCTION AND RATIONALE

1.1 Background

1.1.1 Squamous Cell Carcinoma of the Head and Neck

Head and neck cancer describes a range of tumours that arise in the head and neck region, which includes the oral cavity, pharynx, larynx, nasal cavity, paranasal sinuses, thyroid, and salivary glands. Cancer of the head and neck is the sixth most common type of malignancy, representing approximately 6% of all cases; worldwide, approximately 830,000 patients develop head and neck cancer each year, and approximately 430,000 will die from this disease (Bray et al 2018). Although the head and neck region contains a wide diversity of structures and cell types, the vast majority (>90%) of head and neck cancers arise from the mucosa of the upper aerodigestive tract and are squamous cell in origin (squamous cell carcinoma of the head and neck [SCCHN]).

The median age of diagnosis of SCCHN is in the seventh decade, and there is an approximately two-fold higher incidence in men. Alcohol and tobacco use are thought to be important risk factors implicated in approximately 75% of cases of SCCHN; infection with cancer-causing types of human papillomavirus (HPV), especially HPV type 16, is also an important risk factor for oropharyngeal cancers that involve the tonsils or base of the tongue.

Two-thirds of patients with SCCHN present with locally advanced, Stage III or IV disease, commonly involving regional lymph nodes. Distant metastasis at initial presentation is uncommon, arising in approximately 10% of patients. The 5-year survival for all stages combined on the basis of Surveillance Epidemiology and End Results (SEER) data is about 60%.

The treatment of SCCHN at initial presentation usually comprises a combination of chemotherapy, radiotherapy and/or surgery, which is often considered "definitive". Surgery is a standard treatment for SCCHN but may be limited by the anatomical extent of tumour and desire to achieve organ preservation; radiotherapy is similarly an integral part of primary or adjuvant treatment of SCCHN. Initial chemotherapy regimens are usually reserved for locally advanced disease and typically comprise a combination of platinum plus paclitaxel or fluorouracil.

Treatment is associated with significant morbidity and a relatively static 5-year survival rate of approximately 50% to 60% in patients with HPV-negative (HPV^{-ve}) disease (patients with HPV-positive [HPV^{+ve}] tumours have significantly better survival) (Ward et al 2014, Ferlay et al 2015). At least 50% of patients with locally advanced SCCHN develop locoregional or distant relapses, which are usually detected within the first 2 years of treatment (Argiris et al 2008, Chow 2020). A minority of patients present with locally recurrent, non-metastatic SCCHN that is amenable to salvage surgery and/or re-
irradiation, where long-term survival is possible; however, for the majority of patients, treatment options are limited and historical survival rates have been poor.

In the setting of recurrent and/or metastatic disease (R/M), first-line treatment with platinum combined with fluorouracil or a taxane has typically resulted in a 30% response rate and median progression-free survival (PFS) of 3 to 4 months, and median overall survival (OS) of 6 to 8 months (Gibson et al 2005, Colevas 2006). Addition of the epidermal growth factor receptor (EGFR)-target therapy cetuximab to a platinum-based chemotherapy with fluorouracil (platinum–fluorouracil) has been shown to significantly prolong median OS from 7.4 months (chemotherapy-alone) to 10.1 months (chemotherapy plus cetuximab) with an increase in PFS from 3.3 to 5.6 months (Vermorken et al 2008).

